## 6.2 Summary of Study Design

This is a prospective study that aims to determine the feasibility of PET-MRI scanning of head and neck cancer patients that are immobilised in a radiotherapy treatment shell. It is estimated that ten patients will be recruited to the study. Patients will be registered into the study once they have given informed written consent. All patients who consent to study entry will undergo study screening to confirm eligibility. Patients who are ineligible following screening will not be considered as enrolled in the study and will receive treatment as per their usual clinical care.

## 6.3 Setting for the Project

Patients will initially have their management discussed through the STH central head and neck MDT. The study will be introduced to potentially eligible patients by oncologists when radical radiotherapy is recommended and recruitment to the study will be at Weston Park Cancer Centre, Sheffield. PET-MRI scans will be performed in the dedicated PET-MRI facility in Academic Radiology, Royal Hallamshire Hospital, Sheffield.

## 6.4 Participants

Patients with locally-advanced head and neck cancers who are fit for radical (curative) treatment. This is a single-centre study and we expect to recruit ten patients.

### 6.4.1 Inclusion criteria

To be eligible for inclusion, participants must meet the following criteria:

1. Aged 18 years or over
2. Able to give informed written consent.
3. New diagnosis of biopsy-proven head and neck cancer.
4. WHO performance status  $\leq 2$ .
5. MDT-recommended treatment with radical radiotherapy, with or without concurrent systemic therapy.
6. MRI and PET-CT staging scans for diagnosis.

### 6.4.2 Exclusion criteria

1. Known intolerance/sensitivity to  $^{18}\text{F}$ -2-deoxyglucose or gadolinium-containing contrast agents.
2. Claustrophobia or other contraindications to MRI.
3. Unable to pass through a 55 cm hula hoop.
4. Female patients that are pregnant or breastfeeding.
5. Unable to understand written or spoken English.
6. Patients not undergoing radical intent radiotherapy.
7. Patients with stage 4 or 5 chronic kidney disease or other biochemical abnormalities e.g. uncontrolled blood glucose levels which can have an impact on PET-MRI imaging or contrast administration.

In the last 12 months, 104 patients have been treated with radical radiotherapy (curative intent) for a newly-diagnosed head and neck cancer at Weston Park Cancer Centre, Sheffield. This equates to 8 new patients per month that are potentially eligible for recruitment. We anticipate 1 or 2 patients per month to participate in the study.

The patient population would include Sheffield as well as the peripheral cancer units of Chesterfield, Rotherham, Doncaster and Barnsley. Radiotherapy is planned and delivered centrally at Weston Park Cancer Centre for all patients.

## 6.5 Sample size

The current study is a feasibility study. We estimate that ten patients will be sufficient to determine whether PET-MRI in a radiotherapy immobilisation shell is tolerable to patients with locally-advanced head and neck cancer. A patient tolerability questionnaire obtained from the ten patients will provide subjective qualitative data from a patient's perspective. The retrospective analysis to achieve the secondary objective for patients who tolerate the scan will be used as pilot data to inform larger studies in the future if feasibility is successful.

## 6.6 Recruitment

Patients newly-diagnosed with head and neck cancer who had a PET-CT scan along with a staging MRI scan and CT chest/upper abdomen scans as part of their diagnosis and were recommended radical radiotherapy will be identified in the weekly central Sheffield Head and Neck MDT. Potentially eligible patients will be approached by their oncologist during an out-patient clinic prior to the radiotherapy planning process and the study discussed with them. Interested patients will be given a verbal explanation of the study and a Patient Information Sheet by an authorised trial clinician or research nurse (an individual on the delegation log). Following this, the patient will be given sufficient time (minimum 24 hours) before they are contacted and asked whether they wish to be considered for the study. If they wish to proceed, then they will be seen on their next hospital visit to give informed, written consent. The Principal Investigator or an authorised clinician on the delegation log will witness the patient's signature and countersign the consent form. Patients are free to withdraw their consent at any time without reason; this will not adversely affect their treatment. One copy of the signed consent form will be given to the patient, one kept in the hospital notes and one in the site file.

All staff involved in the consent procedure will have current Good Clinical Practice (GCP) training. In the unlikely event that the patient loses capacity after informed

consent and before the PET-MRI scan, then the patient will be withdrawn from the study in the interest of safety.

Screening logs will be kept for those patients who are given the patient information sheet and were eligible. This data will be considered by the Trial Management Group if there are difficulties in recruiting to the study.

## 6.7 Outcome Measures

### 6.7.1 Objectives and measurement

#### Primary objective

The primary outcome will be the proportion of patients that complete the PET-MRI scan as per protocol whilst immobilised in the radiotherapy treatment shell. For patients that do not complete the full scan, the duration of time in the scanner will be recorded as well as the reasons why they were unable to complete the scan. Patient tolerability questionnaire will provide this qualitative data.

#### Secondary objective

The secondary objective is to assess the impact of the additional PET-MRI scan on the precision of radiotherapy planning. These tests will be conducted retrospectively after conventional radiotherapy planning and do not interrupt a patient's flow through to treatment or their standard care.

#### Co-registration of images for radiotherapy planning:

A PET-MRI scan of each patient provides PET images that are inherently co-registered with MRI images. In order to achieve the secondary objectives, three categories of images are obtained for radiotherapy planning purposes by superimposing images from the PET-MRI scan on to the planning CT scan, a technique termed 'image registration'.

Category 1: Planning CT scan ("CT") with no fusion: this is standard practice

Category 2: Planning CT fused with MRI images from the PET-MRI scan ('CT-MRI')

Category 3: Planning CT fused with PET-MRI images ('CT-PET-MRI')

The secondary objectives are:

1. To compare the radiotherapy target volumes (GTV (gross tumour volume) and CTV (clinical target volume)) contoured in the three categories above (CT, CT-MRI and CT-PET-MRI images). A quantitative assessment will be done by measuring the volumes in three dimensions using Varian's External Beam Planning software in Aria. A qualitative analysis of the 3D dose distribution, comparison of target coverage, conformity, homogeneity and examination of specific dose/volume objectives of organs at risk will be done.
2. Assess inter- and intra-observer variability in treatment contours and precision of target delineation in the three categories above (CT, CT-MRI and CT-PET-MRI scans). This will be assessed using Dice Similarity Index and Hausdorff distance in the three categories.

#### **Exploratory objective:**

To assess whether PET-MRI scanning adds benefit to the cancer patient's diagnostic investigations. Clinical reports of the PET-MRI scan will be compared to reports from staging MRI and PET-CT scans to determine if any new diagnostic information is brought to light by PET-MRI.

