### **Exploratory objective:**

To assess whether PET-MRI scanning adds benefit to cancer patient's diagnostic investigations.

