### 5.3 Potential benefit to patients

The current project is a feasibility study to confirm that PET-MRI scans with immobilisation in a radiotherapy shell are tolerated by head and neck cancer patients. At this stage, it is of no direct benefit to patients enrolled on the study, but, if successful, will provide important pilot data that could be used to plan a larger study in the future.

We do not anticipate that the PET-MRI scan will add any new diagnostic information as all recruited patients would have had similar imaging (MRI and PET-CT) already at the time of diagnosis. However, this is an additional and advanced imaging technique where the PET-MR images are reported by an appropriately-trained radiologist. If there is any significant change that could have an impact on a patient's cancer treatment, this will be communicated to the patient by their Oncologist.

Gaining qualitative perspectives of the participant's experience of undertaking a PET-MRI scan will allow the project team to gain valuable insight into potential barriers that could influence the implementation of this imaging modality into standard clinical practice. This will help the team to develop supportive services which will help future patients to successfully complete the scan as part of their routine standard care. Subsequently, this could provide a long term benefit to future patients by providing them with access to a technology that can potentially aid in improving the precision of radiotherapy planning. This can, in turn, have a positive impact on overall outcomes from cancer treatment; in terms of curing cancer as well as reducing side effects.

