### 6.10.4 Adverse events

All Adverse Events (AEs), Serious Adverse Events (SAEs) and fatal or life-threatening suspected / unexpected serious adverse reactions (SUSARs) that occur during the study, either observed by the investigator or reported by participants, whether or not attributed to the study, will be reported to the DMEC in accordance with current GCP standards. SAEs and SUSARs, and deaths should be reported within 24 hours of becoming aware of the event.

We do not expect any persistent or prolonged adverse effects from the intervention. Participants are monitored for 30 days from recruitment to the study. Standard care involves regular assessments and ongoing treatment of cancer over the next 6-8 weeks and regular post treatment follow up thereafter. Any suspected adverse events from study intervention will be reported to the study team appropriately.

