## Section 7 – Statistical opinion

With this type of feasibility study, it is not necessary to perform formal power calculations, and justification of the number of subjects to be enrolled is provided in section 6.5.

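### The exploratory objective asks whether PET-MRI adds diagnostic benefit, but comparing reports shows only where they differ; new findings should be classed as confirmed, refuted or not verifiable

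*Combined protocol and SAP*

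**What the plan says.** The exploratory objective appears in section 4 and again, with its method, in section 6.7.1: "To assess whether PET-MRI scanning adds benefit to the cancer patient's diagnostic investigations". The method is one sentence: "Clinical reports of the PET-MRI scan will be compared to reports from staging MRI and PET-CT scans", in order "to determine if any new diagnostic information is brought to light by PET-MRI".

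Other parts of the document bear on this:

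- **Section 5.3** expects little yield: "We do not anticipate that the PET-MRI scan will add any new diagnostic information as all recruited patients would have had similar imaging". It also says that a suitably trained radiologist reports the images, and that the oncologist tells the patient of any significant change that could affect treatment.
- **Section 6.10** places the staging MRI and PET-CT a few weeks before recruitment.
- **Section 6.8**, in its readable text, has no analysis for this objective. Its caution about statistical significance covers the secondary objectives only.
- **Section 6.10.4** says that standard care continues through 6-8 weeks of treatment, with "regular post treatment follow up thereafter". The study's own monitoring, in sections 6.10.4 and 6.10.6, lasts about 30 days and is for adverse events.
- **Sections 6.4 and 7** set the size: "This is a single-centre study and we expect to recruit ten patients", and "it is not necessary to perform formal power calculations".

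**The concern.** The question is about benefit, but the method measures disagreement between reports. A new item in the PET-MRI report can arise in three ways: PET-MRI detected something real that the earlier scans missed; something real developed or changed after staging; or the item is wrong, for example inflammatory uptake read as a node. Only the first is a diagnostic gain from the modality. All three look the same when two reports are laid side by side.

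The gap matters most in the situation that section 5.3 expects. If true new information is rare, false items and interval change make up a larger share of whatever is found.

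What is at stake is how the result is used later. Sections 6.5 and 13 treat this study as a source of pilot data for a larger one, and section 12 foresees publication. A statement that PET-MRI revealed new information in some patients could be carried forward as evidence of benefit without anyone having checked whether the information was right.

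**Working it through.** **Is there a figure to reproduce?** No. Section 6.5 gives ten patients as a feasibility estimate without a rate, precision or power, section 7 waives a power calculation, and nothing is stated for the exploratory objective.

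**Does any other section supply verification?**

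| Place | What it provides | Does it check a new finding? |
|---|---|---|
| 6.7.1, exploratory objective | Report compared with report | No |
| 5.3 | Trained reader; treatment-relevant changes told to the patient | No: a clinical step, not an outcome definition |
| 6.8 (readable text) | Nothing on this objective | No |
| 6.10.4 and 6.10.6 | About 30 days of adverse-event monitoring | No |

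**How often might a spurious item appear?** The inputs are n = 10 scans (section 6.4, assuming all are completed and reported) and f, the per-patient probability of a false new item. The documents do not give f, so a range is assumed. Patients are taken as independent.

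P(at least one spurious item) = 1 - (1 - f)^n

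| Assumed f | (1 - f)^10 | P(at least one), n = 10 |
|---|---|---|
| 1% | 0.904 | 10% |
| 2% | 0.817 | 18% |
| 5% | 0.599 | 40% |
| 10% | 0.349 | 65% |
| 20% | 0.107 | 89% |

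The chance reaches one half at f = 1 - 0.5^(1/10) = 0.067, that is 6.7%.

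Some scans may not be completed. With n = 8 the results at f = 5%, 10% and 20% are 34%, 57% and 83%, and the break-even is 1 - 0.5^(1/8) = 8.3%.

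**What share of new items would be false?** Let t be the per-patient rate of true new items, also assumed. The expected false share is f/(t + f). With f = 5%, it is 0.05/0.07 = 71% if t = 2%, 0.05/0.10 = 50% if t = 5%, and 0.05/0.15 = 33% if t = 10%. The lower the true yield, the less an unverified new item means.

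**What would verified counts show?** Exact 95% intervals are 0-31% for 0/10 and 0.3-45% for 1/10. Verification would make the finding interpretable, but ten patients still support only a descriptive statement.

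**The case against.** The strongest reply is that the plan contains no scoring rule. Section 6.7.1 sets no count, threshold or success criterion, and an erroneous item need not qualify as diagnostic information at all. A reader might infer that the plan scores every new report item as benefit. The documents do not support that: the terms are undefined, and counting every new item is only one possible reading. What stands is that the plan offers no way to separate a right item from a wrong one, whichever reading is taken.

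A reader might also infer that some apparent benefit among ten patients is likely by chance. That needs a false-finding rate above about 6.7% per patient, and the documents give no rate. At 1-2% the chance is only 10-18%. Nor is one finding among ten a criterion anywhere in the plan; the calculation only illustrates how exposed the result is.

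A third point concerns the remedy. All participants go on to radical radiotherapy, so a lesion that disappears within the treated area proves nothing either way, and many items may never be verifiable. Section 6.10.4 shows that standard follow-up continues, not that new findings will be biopsied or imaged again. This objection is sound. Crediting only confirmed findings as benefit would replace an overcount with an undercount, so unverifiable items need a class of their own.

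Finally, a figure in section 6.8 is not shown and the data collection tool in Appendix 2 is not in the available text. Either could bear on how findings are recorded. The point therefore rests on the method as written in section 6.7.1.

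**Conclusion.** The point holds in a limited form. The exploratory method detects differences between reports and cannot by itself show diagnostic benefit, because false items and real change since staging are indistinguishable from better detection. This conclusion needs no assumed rate.

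The size does depend on assumptions. For false-finding rates from 1% to 20% per patient, with independent patients and ten reported scans, the chance of at least one spurious new item runs from about 10% to 89%. The documents do not say where in that range the study lies, so no claim that a spurious item is likely is justified.

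The importance is modest. The objective is exploratory, the study has ten patients, feasibility is decided by scan completion, and section 5.3 already expects no new diagnostic information. This is an improvement worth making because it is cheap, not a defect that threatens the study.

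**What to change.** In section 6.7.1, add that each new PET-MRI finding will be classed as confirmed, refuted or not verifiable, using records that standard care already produces: MDT outcome, any pathology, later imaging and follow-up. Report the number of patients with each class out of all patients scanned, as description only.

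Report unverifiable items as new but unconfirmed, neither as benefit nor as error. State that radiotherapy limits verification, so the confirmed count is a lower bound on true added information. Confirmation does not by itself separate better detection from change since staging, so give the time between the scans alongside each item.

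The cost is a short record review for at most ten patients, which fits the analysis period of March 2023 to February 2024 in section 6.15, and a few sentences in the protocol. No study procedure is added. The downside is that some findings will stay unverifiable and the confirmed count may be small.

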#### **6.8 Statistical/Qualitative analysis**

[figure not shown]
- The proportion of patients completing the PET-MRI scan will be recorded that will determine feasibility.
- All recruited patients are expected to complete a questionnaire which will provide a qualitative assessment. Statistical analysis will be completed on the binary and Likert scale questions. This process will allow the study team to identify any issues faced during the PET-MRI scan and the percentage of participants who were affected by these. Thematic analysis will be completed on the open-ended questions. This will allow the project team to explore themes around patient experience, helping the team to understand how

patients may need to be supported during the scanning process if it is to become standard of care.

- As this is a pilot study with ten patients, we do not anticipate this analysis for secondary objectives to provide any statistically significant outcomes. But this will help to specify the kinds of analysis that are possible in a larger study and will also be used to calculate sample sizes.

## 6.9 Intervention

An illustration of the pathway of a patient that is enrolled in the study is shown in the following diagram. Study-specific events are indicated in **red**.

## 6.10 Safety Assessment

Patients that are enrolled in the study will have one additional diagnostic test compared to their normal standard of care, namely, a PET-MRI scan. Patients recruited to the study will have had a standard gadolinium-enhanced MRI scan of the neck as well as a whole-body PET-CT scan with radioactive glucose tracer during their diagnosis of cancer as standard of care a few weeks prior to recruitment into the study. Potential safety issues related to the additional PET-MRI scan are: (i) administration of the MRI contrast agent gadolinium; (ii) administration of radioactive  $^{18}\text{F}$ -2-deoxyglucose; (iii) additional radiation exposure from  $^{18}\text{F}$ -2-deoxyglucose.

### 6.10.1 Administration of Gadolinium

Chelates of the rare earth element gadolinium are used as contrast agents in MRI scans. They improve the conspicuity of abnormal tissue and are considered mandatory in staging head and neck cancers. The current Gadolinium-based contrast agents on the market are considered to be safe: they have a very low rate of immediate adverse events (0.06 – 0.09%) and the incidence of acute severe reactions such as anaphylaxis is very rare (0.0025 – 0.005%). A previous reaction to MRI contrast is an exclusion criterion (see section 6.4.2) and patients with a history of this will not be recruited. Gadolinium can be nephrotoxic when given in large volumes (30 mL) to patients with renal disease/renal impairment. For tumour enhancement in cancer staging 7.5 mL of the macrocyclic chelate gadobutrol (Gadovist, Bayer; 1mmol/mL) is used in Sheffield Teaching Hospitals and this is safe. Linear chelate Gadolinium-containing agents have been associated with nephrogenic systemic fibrosis and there are also concerns regarding Gadolinium retention in the brain following repeated doses of linear chelates. These findings led the European Medicines Agency to suspend use of the linear chelates in 2017. The macrocyclic agents such as Gadobutrol are considered safe even in patients with severe chronic renal impairment. Overall, there is considered to be no extra risk to patients from the MRI component of the PET-MRI scan.

### 6.10.2 Administration of $^{18}\text{F}$ -2-deoxyglucose

PET imaging in oncology is based on the increased uptake of glucose by cancer cells, which have more cell surface glucose transporter proteins and increased

intracellular glycolytic enzyme levels than normal cells. The increased glycolytic rate of cancer cells enables their detection with the fluorine-labelled analogue of glucose,  $^{18}\text{F}$ -2-deoxyglucose. There are no safety concerns with the use of  $^{18}\text{F}$ -2-deoxyglucose, which is in standard use for PET-CT scanning throughout the world.

### 6.10.3 Additional radiation exposure from $^{18}\text{F}$ -2-deoxyglucose

The radioactive isotope  $^{18}\text{F}$  decays by positron emission, having a half-life of 110 min. For 'average' patients, this isotope has an effective radiation dose of 19  $\mu\text{Sv}/\text{MBq}^{14}$ , resulting in an exposure of about 4 – 6mSv from the typical 200 - 300 MBq of  $^{18}\text{F}$  that is used in PET oncology imaging.

| FDG dose reference levels                 |           |           |         |              |
|---|-----------|-----------|---------|--------------|
| Minimum ARSAC Dose Reference Level (DRL): | 100MBq    |           |         |              |
| SPC DRL for GE710 Discovery scanner       | Weight    | DRL       | min/bed | Overlap      |
|   | <115Kg    | 3.5MBq/Kg | 2       | 23
(~50%) |
|   | 115-140Kg | 400MBq    | 2.5     |              |
|   | >140Kg    |           | 3       |              |

This is a standard dose for a diagnostic PET scanning and used widely. Patients will be required to follow radiation protection advice after the scan which includes staying away from pregnant women and young children for about 8 hours while the radioactive tracer can still be in their system.

Patients have their contrast-enhanced radiotherapy planning CT scan as part of standard treatment before the PET-MRI scan. A minimum of 24 hours and maximum of 2 weeks will be maintained between the planning CT scan and the PET-MRI scan.

